4.3 Statistical Design and Power

Sample Size

Given that the primary purpose of the proposed study is to evaluate sucralose and ace-K pharmacokinetics, formal sample size calculations were not performed. In order to conservatively account for 20% attrition, we will recruit a total of 48 lactating women and their infants in order to complete measurements on a planned sample of 40 mother-infant dyads.

Planned Analyses

The concentration-time profile of sucralose and ace-K in plasma and breast milk from mothers will be analyzed by non-compartmental analysis (NCA)³⁵ and through a population pharmacokinetic approach using Pumas V1.0 (Baltimore, MD). Sucralose and ace-K concentrations (ng/mL) in plasma and breast milk will be first graphically explored and summarized descriptively. From the rich plasma and breast milk concentration-time data, NCA analysis will be performed to obtain the following PK parameters such as area under the curve (AUC), clearance, maximum concentration (C_{\max}), time-to-maximum concentration (T_{\max}) and terminal half-life ($T_{1/2}$).

The milk-to-plasma ratio (M:P) will be calculated for sucralose and ace-K. The population PK analysis of sucralose and ace-K in mothers from plasma and breast milk will be performed using the non-linear mixed effect modeling approach.³⁶⁻³⁸ Rich PK samples collected from mothers will be used to estimate the base PK model parameters and to characterize the effect of subject-specific prognostic factors (e.g., weight status, reported LCS consumption habits, overall dietary intake, body weight, maternal blood volume, age, sex, and race/ethnicity) to explain the between subject variability in the PK parameters. Plasma and breast-milk data will be analyzed together in the population PK analyses.

Using the sparse PK samples collected from the infants, a population PK analysis of sucralose and ace-K in infants will be performed, in combination with the robust maternal data.^{39, 40} The PK model in mothers will serve as the starting point for developing the pediatric PK model. Using principles of allometry, the PK parameters will be scaled down to infants using body weight and age maturation factors for the PK parameters.⁴¹

Additional infants' covariates will be evaluated in the combined PK model. The final population PK model for sucralose and ace-K in both mothers and infants will be evaluated and qualified using standard goodness of fit diagnostics and quantitative predictive check methods. The relative infant dose (RID) of sucralose and ace-K will be calculated as described in the FDA lactation guidance.⁴² Given that blood volume differs in obese vs. lean individuals, adjustments for blood volume will be performed by calculating the total mass of sucralose or acesulfame-potassium in breast milk, as in our prior study.⁷

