E. Study Population:

We plan to study 50 lactating mothers and their infants, for a total of 100 participants. Eligibility will be assessed during a phone screening. For eligibility, mothers will have given birth within the past 6 months, be ≥ 18 years of age, and be exclusively breastfeeding. We will limit enrollment to mothers of infants <6 months of age, consistent with recommendations to introduce solid foods. Any individual with a known allergy or contraindication to LCS will be excluded. Only mothers whose infants are ≥ 4 weeks

corrected age will be eligible. Any mothers or infants with an active nutritional disorder known to cause malabsorption will be excluded.

Planned distribution by sex: We will recruit lactating women and their infants. All mothers (n=50) will therefore be female. However, we will recruit infants irrespective of their sex and therefore anticipate that approximately half (n=25) of the total sample of infants (n=50) will consist of females and half (n=25) will consist of males.

- Rationale: This research topic pertains specifically to lactating women because this study aims to measure low-calorie sweetener concentrations in the breast milk. However, findings will pertain to both males and female infants and therefore both boys and girls will be included

Planned distribution by race/ethnicity: Mother-infant dyads will be recruited without bias to race or ethnicity, and eligibility for inclusion within the study will not be determined by these factors. We anticipate the demographic profile of participants will be proportional to the race/ethnic distribution of mothers seen at The GW Midwifery Service.

F. Human Subjects

All of the data collected in this study are collected specifically for research purposes. Data will be provided through self-report of the mother (demographic information, habitual lowcalorie sweetener consumption, infant anthropometry etc.) and collected of biospecimens, including blood and breast milk, as well as measurement of maternal height and weight in the Clinical Research Unit.

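### At the SAP's own 20% attrition, 48 recruited dyads give 38.4 expected completers, not 40, and 48 also differs from the protocol's 50 (minor)

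*SAP*

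**What the plan says.** SAP section 4.3, under Sample Size, gives three linked figures: an attrition rate, a recruitment number and a completer target. It says "In order to conservatively account for 20% attrition, we will recruit a total of 48 lactating women and their infants", the purpose being to "complete measurements on a planned sample of 40 mother-infant dyads". The same paragraph says that "formal sample size calculations were not performed", because the study is mainly a pharmacokinetic description.

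Protocol section E (Study Population) gives a different number: "We plan to study 50 lactating mothers and their infants, for a total of 100 participants". It repeats that figure in the planned distribution by sex, with 50 mothers and 50 infants, the infants expected to divide into about 25 girls and 25 boys. The protocol gives no attrition rate and no completer target.

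**The concern.** There are two faults. First, the SAP's three figures do not fit together. An allowance for 20% attrition should leave the target number after 20% of those recruited are lost, and 48 does not. The SAP also describes its allowance as conservative, whereas the shortcut used under-recruits.

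Second, the two documents give different enrolment numbers, and nothing in the text supplied explains why. One part of the SAP was not available, so a reconciling statement there cannot be excluded, but it would not alter the arithmetic of the sentence in section 4.3.

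What is at stake is modest. The recruitment number tells the site when to stop enrolling, and it is the figure against which actual enrolment will later be reported. There is also limited slack on the infant side. Each infant gives one plasma sample in one of five time windows (protocol section D), so 40 completers would average 40/5 = 8 infants per window if spread evenly, which is an assumption.

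**Working it through.** **Inputs**

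- Attrition d = 20% (SAP 4.3)
- Recruited N = 48 dyads (SAP 4.3)
- Target completers n = 40 dyads (SAP 4.3)
- Planned number in the protocol = 50 dyads, 100 participants (protocol section E)
- No alpha, power, effect size or standard deviation is given, so only the attrition step can be checked.

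**Reproducing the SAP's figure**

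n × (1 + d) = 40 × 1.20 = 48. This matches exactly, so the 48 appears to come from adding 20% of the target to the target.

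**Number needed if 20% of those recruited are lost**

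n / (1 − d) = 40 / 0.80 = 50.

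**Expected completers, N × (1 − d)**

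- N = 48: 48 × 0.80 = 38.4, which is 1.6 below 40 (1.6/40 = 4%).
- N = 50: 50 × 0.80 = 40.0.

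**Attrition at which 48 still yields 40**

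1 − 40/48 = 8/48 = 16.7%.

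**Chance of reaching 40**

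Assume that each dyad drops out independently with probability 0.20. The number completing is then binomial(N, 0.80), and P(X ≥ 40) = Σ C(N, k) × 0.80^k × 0.20^(N−k), summed over k = 40 to N.

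- N = 48: 0.358
- N = 50: 0.584

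**Effect on precision**

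For an estimate whose standard error scales with 1/√n, the ratio is √(40/38.4) = 1.021, about 2% larger.

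**Comparison of the documents**

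| | SAP 4.3 | Protocol E |
|---|---|---|
| Dyads | 48 to recruit | 50 to study |
| Attrition rate | 20% | not stated |
| Completers | 40 | not stated |
| Expected completers at 20% | 38.4 | 40.0 |

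The protocol's 50 equals 40/0.80, but the protocol does not say it was obtained that way, so the agreement is numerical only.

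**The case against.** The strongest objection is that nothing analytic depends on 40. There is no power or precision claim, and the expected gap is 1.6 dyads. That stands, and it is why the point is minor.

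A second objection is that completers are a poor measure of information here. The planned population model can generally use partly observed participants, and most maternal samples are taken during the supervised 8-hour visit. Only the 12-hour milk sample and the 24-, 48- and 72-hour collections come later. A dyad lost after the visit would still supply most of its profile. This is fair: the loss of data may be smaller than the loss of completers. It does not repair the SAP sentence, which is framed in completed dyads and does not define attrition or say how partial dyads count.

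Third, the wording allows other readings. *Conservatively* could describe 20% as a cautiously high rate, with true attrition expected to be lower. The 20% could also mean a margin of 20% of the target (8/40), which gives 48 exactly. Neither reading is stated, and the second is not the usual meaning of attrition. Under the first, 48 is enough only if actual attrition is at most 16.7%, so it still does not cover the stated 20%.

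Fourth, the two numbers may come from different versions. The protocol is dated April 9th, 2024, and the available SAP text carries no date, so which number governs cannot be established. That supports reconciling them; it does not support leaving both.

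Finally, the binomial figures rest on independent dropout at exactly 20%, and even 50 recruits miss 40 about 42% of the time (1 − 0.584). They are an illustration only; the error is shown by the expected counts.

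**Conclusion.** The point holds and is minor. As written, the SAP's 48 does not deliver its 40 completers at its stated 20% attrition: the expected number is 38.4, and 40 is reached only if attrition is 16.7% or less. This takes attrition in its usual sense, as a share of dyads recruited. Separately, and however attrition is read, the SAP's 48 and the protocol's 50 disagree with no explanation in the available text.

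The shortfall in expected completers arises only if enrolment stops at 48. If the protocol's 50 is followed, the expected number is 40 and only the SAP's figure needs correcting. In neither case would the planned analyses or the interpretation of the study change.

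**What to change.** State one recruitment number in both documents, and say in the SAP that attrition is a share of dyads recruited. There are two ways to do this.

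- **Use 50.** Change 48 to 50 in SAP section 4.3. This agrees with the protocol and with 40/0.80. Because 50 gives exactly 40 on expectation, with no margin, the word *conservatively* should be dropped or tied explicitly to the choice of the 20% rate. The cost is a one-number edit and a small wording change, with no participants beyond those the protocol already plans.
- **Keep 48.** Restate the SAP allowance as 16.7% attrition, or as about 38 completers at 20%, and change the protocol's counts in section E (50 mothers, 50 infants, 100 participants, 25/25 by infant sex) to match. The cost is text edits in both documents.

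The first is the smaller change. In either case, one sentence defining a completed dyad, and saying that partly observed dyads stay in the population model if that is the intention, would make the target unambiguous.
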